Day 43-50/Visit 4: Subjects will be asked to withhold morning dose of the study drug the day of the study visit. Women of child bearing potential will have a negative pregnancy test confirmed. Subjects will be asked to complete an ACT to assess asthma control and a validated asthma quality of life questionnaire (Juniper mini AQLQ). FeNO will be measured using a Circassia Niox Vero machine with disposable filters. Basic spirometry will be performed, Methacholine test will be performed if subject meets safety criteria ($FEV_1 > 1.5L$ or 60% predicted). 10ml of blood will be collected for measurement of cytokines, biomarkers and blood eosinophil count. For those patients in PK group, an additional 35 ml of blood will be collected over an additional 7 times points (pre-dose, 0.5 hour, 1 hour, 2 hour, 3 hour, 4 hour, and 8 hour). Study drug will be administered in the clinic after the pre-dose PK blood draw.

Unused study medication will be collected and pill count will be recorded.

Day 71-78/Visit 5: Subjects will be asked to withhold morning dose of the study drug the day of the study visit. Women of child bearing potential will have a negative pregnancy test confirmed. Subjects will be asked to complete an ACT to assess asthma control and a validated asthma quality of life questionnaire (Juniper mini AQLQ). FeNO will be measured using a Circassia Niox Vero machine with disposable filters. Basic spirometry will be performed. Methacholine hyperresponsiveness will be measured if subject meets safety criteria ($FEV_1 > 1.5L$ or $>60\%$ predicted). 10ml of blood will be collected for measurement of cytokines, biomarkers and blood eosinophil count. For those patients in PK group, an additional 35 ml of blood will be collected over an additional 7 times points (pre-dose, 0.5 hour, 1 hour, 2 hour, 3 hour, 4 hour, and 8 hour). Unused study medication will be collected and pill count will be recorded. Study drug will be administered in the clinic after the pre-dose PK blood draw.

Sample Size and Population

Adults 18 and older, with physician diagnosed mild to severe persistent asthma will be screened. 36 participants will be randomized equally into two arms (18 per group); 1 gram of oral ginger extract twice a day for 28 days or matching placebo. Our sample size analysis requires 16 participant per group and with an anticipated 10% attrition rate, we will enroll 18/group.

Randomization will not be stratified in this pilot study.

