1. STUDY OBJECTIVES

1.1 Primary Objective

The primary endpoints are a clinically significant improvement in tolerance to inhaled methacholine (PD20) or a clinically significant decrease in exhaled nitric oxide. A clinically significant increase in tolerance to inhaled methacholine is defined as a 0.7 increase in the doubling dose for inhaled methacholine from the subjects baseline. A clinically significant decrease in exhaled nitric oxide is defined as a 20% decrease in subjects starting at a baseline of >50 ppb or a decrease of 10 ppb for subjects starting at a baseline of <50 ppb.

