3. STUDY DESIGN

A placebo controlled, double blind, randomized clinical pilot study of mild to severe asthmatics treated in a 1:1 ratio with oral ginger 1 gm twice per day or matching placebo.

18 subjects will be assigned to each of two arms (ginger vs. placebo). This is defined by a power analysis requiring 16 subjects per arm and a 10% projected attrition rate. Subjects will be evaluated 5 times during the study, at screening, baseline methacholine testing, at the initial randomization visit and at days 28 and 56 while taking ginger or placebo.

The primary outcomes will be the improved tolerance to the bronchoconstrictive effect (reduced airway hyperresponsiveness) of inhaled methacholine (methacholine PD₂₀) or a reduction in exhaled nitric oxide. Secondary outcomes will include an improvement in baseline FEV1 of 100ml, a reduction in eosinophilia or a reduction in asthma associated serum cytokines. An additional secondary outcome will be defining the pharmacokinetic profile of active components of ginger in adult asthmatics.

Grant phase	Spec. Aim	Primary outcome	Clinically Significant Change [ref]	Means ± S.D; examples from literature [ref] (units)	Sample Size \group	# of groups	Sample size required	Sample Size required with 10% attrition
R61	1	Mch PD ₂₀ doubling dose	Increase of 0.7 in Mch doubling dose ¹²	1.07 ± 0.6 1.73 ± 0.6 (Mch doubling dose) ¹²	14	2 2g/day ginger placebo	28	32
	2	Exhaled nitric oxide	20% decr for >50 ppb or decr of 10ppb for <50ppb ¹³	74 ± 37 37 ± 34 (ppb) ¹⁴	16	2 2g/day ginger placebo	32	36 for aims 1&2

Outpatient; The John Edsall-John Wood Asthma Center at the Columbia University Medical Center

Individual enrollment: 78 +/- 7 days. Enrollment period 12 months, Entire trial (first subject screened to last patient completed): 20 months.

Screening/Run-In Period

Adults 18 and older, with physician diagnosed mild to severe persistent asthma will be screened. After reviewing and signing informed consent, subjects that fulfill inclusion and exclusion criteria will be invited to participate.

Day 0/Visit 1: Screening Visit: review of medical history, recording of medication use, physical exam by study MD or NP, scoring on ACT and basic spirometry before and after bronchodilator. Subjects will then be asked to continue their usual asthma medications for the 14-21 day run-in period.

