Day 14-21/Visit 2: Subjects will be asked to withhold appropriate short and long acting bronchodilators for the appropriate period. Women of child bearing potential will have a urine pregnancy test checked. Checklist for methacholine will be reviewed with patient. If ACT remains ≤ 19 and FEV1 > 60% predicted, subjects will undergo methacholine bronchoprovocation testing which involves inhaling increasing concentrations of nebulized methacholine until the measured FEV1 decreases by 20% of the initial value measured after diluent inhalation, defined as the methacholine PD20. If ACT is > 19, consistent with good asthma control, subjects will be terminated from the study.

Day 15-23 (1-2 days following V2)/Visit 3 Randomization Visit:

If ACT remains ≤ 19, subjects will be randomized into one of two treatment groups; oral ginger (1g twice per day: Pure Encapsulations™) or matching placebo (*FDA IND in place: # [REDACTED]*). Ratio of randomization will be 1:1.

At the randomization visit women of child bearing potential will have a negative pregnancy test confirmed, subjects will be asked to complete an ACT to assess asthma control and a validated asthma quality of life questionnaire (Juniper mini AQLQ). Fractional excretion of nitric oxide (FeNO) will be measured using a Circassia Niox Vero machine with disposable filters. Pre-dose basic spirometry will be performed. 10ml of blood will be collected for measurement of baseline cytokines, biomarkers and blood eosinophil count. Subjects will be given their first dose of study drug and post-dose spirometry will be repeated one hour later.

A subset of subjects (4 males and 4 females) will undergo pharmacokinetic (PK) measurements of the key metabolites of active ginger components. For those patients, an additional 35 ml of blood will be collected over an additional 7 times points (pre-dose, 0.5 hour, 1 hour, 2 hour, 3 hour, 4 hour, and 8 hour).

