9.2 Sample Size and Randomization

We utilized published literature to identify the magnitude of change in our primary outcomes that are clinically relevant. As illustrated in the table in section 3, we calculated a need of 14 subjects per arm for the methacholine measurement and 16 subjects per arm for the exhaled nitric oxide assessment (same subjects studied in methacholine and exhaled nitric oxide assays). Thus we need 16 subjects per arm and anticipate a 10% attrition rate overall requiring 36 subjects. As illustrated in the table in section 3, an enhanced tolerance to inhaled methacholine of 0.7X the doubling dose is considered clinically significant.¹² We anticipate a S.D. of 0.6 in both groups and aim to achieve 80% power at the 0.05 significance level. This requires 14 subjects for each of the two arms. For exhaled nitric oxide with baselines starting at >50ppb, a 20% decrease is considered clinically significant. We expect a S.D. of ~ 37 and aim to achieve 80% power at the 0.05 level and will thus require 16 subjects for each of two arms.

Treatment Assignment Procedures

Subjects will be randomized to treatment A or B in a blinded fashion using the randomization algorithm within REDCap. The randomization module in REDCap implements a defined randomization model within the project, allowing the site to randomize the subjects. In this module, randomization model is defined as Drug A and Drug B in a 1:1 ratio. Drug A and Drug B may refer to placebo or active drug, however they are left coded as such to ensure blinding. The module creates a template allocation table, which the user uses to structure the randomization table to be imported. The module also monitors the overall allocation progress and assignment of randomized subjects to ensure balanced proportions of active drug and placebo. Only one site member will be allowed randomization privileges, but the site will confirm, and lock the specific data field to ensure that no data is altered after randomization. There is no stratification, and there are no variable block sizes.

Trial randomization codes for each individual subject will be retained within the REDCap data set as treatment A or B. The independent statistician retains the identity of A or B and does not disclose this to the study conductors. The planned breaking of the code will occur after data analysis is complete. Unplanned breaking of the code will occur if a medical condition mandates such an action.

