9.6 Data Analyses

We will compare the change in log-transformed methacholine reactivity (PD₂₀) in the ginger versus the placebo group using two-sample t-test. We will compare patients' initial PD₂₀ (day 0) to their subsequent PD₂₀ at days 28, 56 using paired t-test. It is possible that the PD₂₀ measurements on days 0, 28 and 56 could be influenced by the consumption of oral ginger 1 hour prior so we will also compare the PD₂₀ at

day 0 to those at 28 and 56. An acute benefit in methacholine tolerance will be reflected in a significant improvement between PD₂₀'s at days 0, 28 and 56 while a chronic improvement will be reflected in improved PD₂₀'s at days 28 and 56 compared to day 0.

Patients with asthma have remarkably consistent fractional exhaled nitric oxide (FeNO) levels when measured over time with mild-moderate asthmatics having FeNO values of approximately 40 ± 10 ppb.²² We will consider a 25% change in FeNO as biologically significant²³ comparing each patient's initial FeNO to their subsequent FeNO at days 28, 56 using paired t-test.

Data from prior studies does not support the existence of significant differences in the intervention effect between subgroups and thus subgroup analysis will not be performed.

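### Section 9.6 reads acute and chronic PD20 benefit from before/after comparisons without placebo; the conclusion should rest on the between-arm test already in that section

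*Combined protocol and SAP*

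**What the plan says.** Section 9.6 plans two PD20 analyses. The first is controlled: "We will compare the change in log-transformed methacholine reactivity (PD₂₀) in the ginger versus the placebo group using two-sample t-test". The second is a paired t-test of each patient's day 0 value against days 28 and 56. It is not said to be on the log scale, or to be run separately by arm.

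The interpretive sentence follows. Acute benefit is read from significant improvement between days 0, 28 and 56, "while a chronic improvement will be reflected in improved" PD20 values at days 28 and 56 relative to day 0. Placebo does not appear in that sentence, and acute and chronic are judged from the same three visits.

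Section 1.1 takes the same before/after view. A clinically significant increase in tolerance is "defined as a 0.7 increase in the doubling dose for inhaled methacholine from the subjects baseline". Section 9.5.1 makes a clinically significant change in PD20 one of the two primary outcomes and does not say how it is compared between arms.

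The sample size table in Section 3 gives the literature example as "1.07 ± 0.6 1.73 ± 0.6 (Mch doubling dose"), with no label for arm, and none for change or level. Section 9.2 adds: "We anticipate a S.D. of 0.6 in both groups and aim to achieve 80% power at the 0.05 significance level". It continues: "This requires 14 subjects for each of the two arms".

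**The concern.** A before/after comparison credits the drug with everything that happens between the two measurements. Here there is reason to expect some movement without drug. Section 4.1, item 3 admits subjects on an upper limit of PD20 at Visit 2 (below 16 mg/ml if taking ICS, below 8 if not). In the Section 6.1 schedule Visit 2 is the only methacholine test before treatment, so the value that admits the subject is also the baseline. (Sections 9.1 and 9.5.1 place the baseline at Visit 3, where the schedule has no methacholine test.) Selecting on an upper limit and then measuring again tends to raise the mean in both arms. Better use of usual inhalers during a trial would act in the same direction.

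The plan does not say that the two-sample result takes precedence over the paired ones. A report that followed 9.6 literally could therefore state a chronic improvement on ginger, or count ginger subjects reaching 0.7 from baseline, while the between-arm test showed nothing. That would be an uncontrolled claim on a primary outcome of a placebo-controlled trial.

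**Working it through.** **Inputs.** SD 0.6, power 80% and alpha 0.05 (Section 9.2; two-sided assumed, since sidedness is not stated). Allocation: "Ratio of randomization will be 1:1" (Section 3). Sixteen evaluable subjects per arm, raised to 18: "with an anticipated 10% attrition rate, we will enroll 18/group" (précis). Example values 1.07 and 1.73 (Section 3 table).

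**The plan's own figure.** For a two-sample t-test with difference 1.73 − 1.07 = 0.66 and SD 0.6, the standardised difference is 0.66/0.6 = 1.10 and the solution is n = 14.00 per arm (power 79.99% at 14). With a difference of 0.7 the solution is 12.6, so 13. The stated 14 therefore matches 0.66 used as a difference between two means.

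**Paired test when ginger has no effect.** Let both arms gain g doubling doses on average, with SD of change 0.6 (assumed; the documents do not say that 0.6 is the SD of a change) and n = 16. The standard error is 0.6/√16 = 0.15, the noncentrality is g/0.15, and the two-sided 5% critical value on 15 df is 2.13. The last column is P(Z ≥ (0.7 − g)/0.6), the share of subjects who individually reach +0.7.

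| Shared gain g | Noncentrality | Paired test significant | Subjects reaching +0.7 |
|---|---|---|---|
| 0 | 0 | 5% | 12% |
| 0.1 | 0.67 | 10% | 16% |
| 0.2 | 1.33 | 24% | 20% |
| 0.3 | 2.00 | 46% | 25% |
| 0.5 | 3.33 | 88% | 37% |
| 1.07 | 7.13 | above 99.9% | 73% |

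The last row applies only if the lower value in the Section 3 table is an arm's gain from baseline.

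**Sensitivity to the SD.** With an SD of change of 1.0 the standard error is 0.25. A gain of 0.3 (noncentrality 1.2) is then significant with probability 20%, 0.5 (noncentrality 2.0) with 46%, and 1.07 (noncentrality 4.28) with 98%.

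**Between-arm test in the same situation.** With both arms simulated at a gain of 1.07, SD 0.6 and 16 per arm (100,000 trials), the two-sample t-test rejected in 5.0% and the paired test in the ginger arm in about 100%. A shared gain cancels in the two-sample test, so its 5% holds whatever g is.

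**The case against.** The strongest reply is that the controlled analysis is already there and comes first. The trial is sized on two arms, Section 9.3 makes intention-to-treat on all randomized subjects primary, and the paired sentences seem meant to separate acute from chronic effects rather than to decide efficacy. This stands, and it limits the point to interpretation: the design and the main test are sound. It does not remove the point, because 9.6 attaches the words about benefit and improvement to the before/after comparison and gives no order of precedence.

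A reader might go further and infer that, on the plan's own example data, placebo alone gains 1.07 doubling doses and so would pass both the paired test and the 0.7 criterion. The documents do not support that. The Section 3 cell labels neither arm nor change. The mention in Section 9.2 of an SD for both groups favours reading the two values as arm means, but a before/after pair (1.07 to 1.73) gives the same 0.66 and the same 14. The FeNO row of the table, 74 ± 37 and 37 ± 34 ppb, reads as levels, and it too goes through a two-sample formula: the difference is 37, the pooled SD is √((37² + 34²)/2) = 35.5, and n = 15.5, so 16. Reproducing 14 therefore does not show that 1.07 is a gain. Even if it is, 27% of such subjects would miss 0.7.

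Nor does 0.7 have to be redefined as a between-arm difference. A threshold from the subject's own baseline is legitimate when the proportions reaching it are compared between arms.

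Regression to the mean is right in direction, but its size cannot be computed, because the documents give no within-subject PD20 variability.

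**Conclusion.** The point holds as a defect of interpretation. The acute and chronic readings in 9.6 and the from-baseline criterion in 1.1 cannot tell a ginger effect from a gain shared with placebo. The false-claim rate depends on a placebo change that the documents do not give. At an assumed SD of change of 0.6 and n = 16 it is 24% to 88% for shared gains of 0.2 to 0.5 doubling doses, against a nominal 5%. It is near certainty at 1.07, a figure that is conditional on an unlabelled table value. A larger SD lowers these rates. The two-sample test in the same paragraph is valid and keeps 5% error when both arms gain equally. The correction is worth making before analysis, but it does not put the design or the sample size in question.

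**What to change.** In 9.6, state that PD20 efficacy conclusions, including any about acute or chronic effect, rest on the ginger-minus-placebo difference in change of log PD20. Keep the paired comparisons on the log scale, by arm, as description only, and reword the acute/chronic sentence to match. If the 0.7-from-baseline criterion in 1.1 is kept, add that the proportion of subjects reaching it is compared between arms. In the Section 3 table, label the two PD20 values by arm and as change or level.

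The cost is a few sentences in 9.6, one in 1.1 and a table label. No new data, visits or subjects are needed.

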9.3 Definition of Populations

Adults aged 18 years and above, with mild to severe persistent asthma will be enrolled. Subjects will have asthma which is not optimally controlled despite the current use of inhaled corticosteroids with or without inhaled long-acting beta agonists. The populations will be those subjects randomized to the placebo arm versus ginger extract arm.

All randomized subjects will be included in the primary analysis, analyzed based on intention-to-treat. In addition, a secondary analysis based on per protocol will be conducted. Per protocol analysis will exclude patients who missed 30% or more of their assigned treatment. Please refer to section 5.4 for the equation to calculate compliance.

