9.5.1 Primary Outcome

The primary outcomes are a clinically significant change in tolerance to inhaled methacholine (PD₂₀) or a clinically significant change in exhaled nitric oxide. These outcomes will be measured at visit 3 (baseline) and visits 4 and 5 (days 28 and 56 of the oral ginger or placebo consumption).

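### FeNO, one of two either/or primary outcomes, has only a within-patient paired t-test in section 9.6, so its stated analysis does not use the placebo arm

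*Combined protocol and SAP*

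**What the plan says.** Section 1.1 joins the two primary endpoints by 'or': a gain in PD20 "or a clinically significant decrease in exhaled nitric oxide". Section 9.5.1 gives the timing: "These outcomes will be measured at visit 3 (baseline) and visits 4 and 5", that is, baseline and days 28 and 56 of treatment.

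Section 9.6 gives PD20 two analyses. Change in log PD20 is compared "in the ginger versus the placebo group using two-sample t-test", and each patient is also compared with their own baseline by paired t-test. FeNO gets only the second kind, "comparing each patient's initial FeNO to their subsequent FeNO at days 28, 56 using paired t-test", with a 25% change called biologically significant. The same paragraph opens with a statement about stability: "Patients with asthma have remarkably consistent fractional exhaled nitric oxide (FeNO) levels when measured over time".

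Elsewhere the plan points to a comparison of arms but names no test. Section 9.3 says "The populations will be those subjects randomized to the placebo arm versus ginger extract arm" and calls for intention-to-treat. Section 9.2 sizes FeNO by arm: it "will thus require 16 subjects for each of two arms".

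**The concern.** Section 9.6 treats the between-arm and within-patient tests as different analyses, because it lists both for PD20. For FeNO only the within-patient test appears. That test asks whether FeNO changed from baseline, not whether it changed more on ginger than on placebo. Section 9.6 does not say whether it is run in each arm or on all patients together; neither gives a ginger-versus-placebo contrast.

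FeNO alone can meet the primary endpoint, so a placebo-controlled trial could have a primary outcome judged without its control. Running the paired test in each arm and comparing the two verdicts is no repair, since 'significant on ginger, not on placebo' does not test the difference between arms. While the between-arm test stays unwritten, the choice between the two kinds of result can also be made after the data are seen.

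**Working it through.** **1. What the FeNO sample size assumes.** Inputs: 74 ± 37 and 37 ± 34 ppb (table in section 3); SD about 37, 80% power, 0.05 level (section 9.2). Two-sided testing is assumed, as the plan does not say.

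- Normal formula with SD 37: n = 2 × (1.96 + 0.84)² × (37/37)² = 15.7, so 16 per arm.
- t-based with pooled SD: √((37² + 34²)/2) = 35.5; d = 37/35.5 = 1.04; n = 15.5, so 16 per arm. Power is 81.3% at 16 and 78.6% at 15.
- Attrition: 32/0.9 = 35.6, so 36 in total, as stated.
- A paired test with the same difference and SD would need 9.3, so 10 patients.

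The stated 16 per arm is therefore a two-sample figure. The test in 9.6 is not the one the trial was sized for.

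**2. What a paired test would do if both arms moved together (hypothetical).** The documents give no common shift, no baseline-to-follow-up correlation r and no SD of change, so all three are assumed. SD of change = 37 × √(2(1 − r)). With no ginger effect and n = 16, the paired test has 15 degrees of freedom and noncentrality √16 × fall / SD of change. For example, a 10 ppb fall with r = 0.5 gives 4 × 10/37 = 1.08.

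| Assumed r | SD of change (ppb) | No common fall | 5 ppb fall | 10 ppb fall |
|---|---|---|---|---|
| 0.5 | 37.0 | 5% | 8.0% | 17.3% |
| 0.8 | 23.4 | 5% | 12.6% | 36.0% |
| 0.9 | 16.5 | 5% | 20.5% | 61.8% |

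The entries are chances of significance in the ginger arm read alone. The 5% counts both directions; in the direction of a fall it is 2.5%.

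If placebo is tested too, 'significant on ginger, not on placebo' has probability p(1 − p). At these three correlations that is 7.4% to 16.3% for a 5 ppb fall and 14.3% to 23.6% for 10 ppb.

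**3. The between-arm test.** A common fall cancels in the difference between arms, so the noncentrality is zero and the two-sample test of change stays at 5% at one visit. If significance at either day 28 or day 56 counted, simulation (60,000 trials, equal correlation between visits, r from 0.5 to 0.9) gives about 9%. The replacement text must therefore name one deciding visit.

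**4. Power of the between-arm change-score test, 16 per arm, on a single SD basis.**

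| Assumed r | SD of change (ppb) | True difference 37 ppb | True difference 14.8 ppb (20% of 74) |
|---|---|---|---|
| 0.5 | 37.0 | 78% | 19% |
| 0.8 | 23.4 | 99% | 41% |
| 0.9 | 16.5 | >99% | 69% |

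The 81.3% in step 1 rests on the SD of single FeNO values and should not be set beside these figures.

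**The case against.** The strongest reply is that a between-arm test was plainly intended and a sentence was left out. Section 9.3 sets placebo against ginger, section 9.2 sizes two arms, and the analysts stay blinded until analysis is complete (9.2 and 9.5). Sections 6.2.3 and 9.2 also expect both primary outcomes to vary in both arms and to inform only in aggregate. All of this stands as evidence of intent, but none of it supplies the test.

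A second reply is that FeNO is stable, so a common shift is unlikely. Section 9.6 says so, and 10 ppb is large: it is the whole clinically significant change for a baseline under 50 ppb. The 62% needs that large fall together with a high correlation. This limits the illustration but leaves the gap in the text.

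A reader might infer that the plan would declare success on a significant paired test in the ginger arm alone, or that the sponsor chose an uncontrolled analysis. The documents support neither. They state no deciding rule for FeNO, and the surrounding design points to a comparison of arms. Nor do they support reading 8% to 62% as this trial's false-positive rate.

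**Conclusion.** The point holds as an omission in the analysis section: followed literally, 9.6 cannot attribute a change in FeNO to ginger. That conclusion rests on the text and on the reproduced sample size, and needs no assumption about drift. The error rates do need one: about 8% to 62% against 5% under an assumed common fall of 5 to 10 ppb and SD of change of 16.5 to 37 ppb, and no excess if FeNO does not move in the placebo arm.

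It should be corrected before unblinding. Three matters nearby are separate and not argued here: the gap between the 20% decrease cited in 9.2 and the 37 ppb used for sizing, the differing FeNO thresholds (25% in 9.6; 20% or 10 ppb in 1.1), and the secondary outcomes with no test in 9.6.

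**What to change.** Replace the FeNO test in section 9.6 with:

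> The primary FeNO analysis compares change from the Visit 3 baseline to day 56 (Visit 5) between ginger and placebo by two-sample t-test, as for PD20; day 28 and the within-arm paired tests are supportive.

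ANCOVA adjusted for baseline FeNO is an acceptable alternative if it is chosen in advance. If power is quoted beside this test, keep to the change-score basis and state the assumed correlation: 78% to >99% for 37 ppb and 19% to 69% for 14.8 ppb, for r from 0.5 to 0.9.

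The cost is one sentence. It needs no new data, visits or patients, and 16 per arm already matches the between-arm test. What the team gives up is the paired test's apparent advantage: 32% to 92% power for a 14.8 ppb fall in the ginger arm, which it has only because it leaves out the placebo arm.

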5.3.1 Allowed Interventions

Subjects will continue their usual asthma medications during the study except for the washout periods listed in section 4.1. Patients will continue their inhaled corticosteroids with or without inhaled long acting beta agonists and/or long acting anti-muscarinic medications. Additional asthma medications (e.g. montelukast) are also allowed. Rescue of asthma symptoms with short-acting beta agonists is also allowed and if this occurs within a washout period, the study visit will be re-scheduled. Subjects who are not excluded due to the use of anti-coagulants will continue the use of all other prescribed medications.

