9. STATISTICAL CONSIDERATIONS

9.1 General Design Issues

We hypothesize that the oral consumption of Pure Encapsulation® ginger extract (2g/day by adult patients with moderate to severe asthma despite normal maintenance medications, will have an improvement in their tolerance to inhaled methacholine or a reduction in lung inflammation over the 56 day treatment period.

This is a randomized, double blind, placebo-controlled design. Patients will have baseline measurements of their pulmonary function and inflammation status and will then be randomized to ginger extract or placebo. The same measurements of pulmonary function and inflammation status will be repeated at 28 and 56 days of ginger or placebo consumption. The durations of 28 and 56 days were chosen because it is hypothesized that the primary benefit of consumption of oral ginger will be an anti-inflammatory effect in

the lung that over time results in improved pulmonary function.

Primary hypotheses: are that the oral daily consumption of ginger will improve the tolerance to inhaled methacholine and/or a reduction in exhaled nitric oxide.

Secondary hypotheses: are that an additional measure of pulmonary function will improve (an increase in baseline FEV1) and/or that secondary measures of inflammation (eosinophilia, asthma associated cytokines) will improve.

Primary outcome measures: The primary outcome measures are methacholine (PD20) and exhaled nitric oxide. These outcomes will be measured at visit 3 (baseline) and visits 4 and 5 (days 28 and 56 of the oral ginger or placebo consumption).

Secondary outcome measures: A clinically significant increase in baseline FEV1 of 100ml. For subjects with eosinophilia (>300 cells/ul) a 32% decrease in blood eosinophils¹⁷, a 40% decrease in serum IL4^{18,19}, a 50% decrease in serum IL5²⁰ or a 75% decrease in serum IL13.²¹

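### Exhaled nitric oxide is a primary outcome, but Section 9.6 gives it only a paired before/after t-test and no ginger-versus-placebo comparison

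*Combined protocol and SAP*

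**What the plan says.** Sections 1.1, 9.1 and 9.5.1 make methacholine PD20 and FeNO the primary outcomes. Sections 1.1 and 9.5.1 join them by *or*. The primary hypothesis in 9.1 is that ginger "will improve the tolerance to inhaled methacholine and/or a reduction in exhaled nitric oxide".

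Section 9.6 treats the two outcomes differently:

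- **PD20:** the change in log PD20 is compared "in the ginger versus the placebo group using two-sample t-test". Paired tests over time are listed in addition.
- **FeNO:** the only test is a paired one, of each patient's "initial FeNO to their subsequent FeNO at days 28, 56 using paired t-test". The sentence names neither arm.

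The rest of the plan is comparative. Section 9.3 states: "The populations will be those subjects randomized to the placebo arm versus ginger extract arm". Section 9.2 says of FeNO "We expect a S.D. of ~ 37" and that the trial "will thus require 16 subjects for each of two arms".

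The FeNO relevance thresholds also differ. Sections 1.1 and 3 use a 20% fall above 50 ppb or a 10 ppb fall below it. Section 9.6 says: "We will consider a 25% change in FeNO as biologically significant".

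**The concern.** A paired test asks whether FeNO moved from baseline. It can be run within the ginger arm or on everyone together, since the sentence does not say which. Neither version is a randomised contrast, and neither separates ginger from change that would have occurred on placebo.

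Some shared change is plausible. Patients enter with suboptimal control, and under 5.3.1 "Patients will continue their inhaled corticosteroids with or without inhaled long acting beta agonists"; they may use these more regularly while under observation. Placebo response and season are other routes. Section 6.2.3 itself expects both primary outcomes to vary over the study in both arms.

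Because the primary outcomes are alternatives, a significant fall in FeNO alone could be reported as a positive trial without any comparison with placebo.

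**Working it through.** **1. Reproduce the plan's FeNO sample size.** Inputs: means 74 and 37 ppb, so a difference of 37 (Section 3 table); SD 37, 80% power and 0.05 level (Section 9.2). Two-sided testing is assumed.

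n per arm = 2 × (1.960 + 0.842)² × (37/37)² = 15.7, which rounds up to 16.

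This matches the stated 16. With the noncentral t instead of the normal approximation, the answer is 17 at SD 37, or 16 at the pooled SD √((37² + 34²)/2) = 35.5. A paired t-test with a mean change of 37 and SD of change 37 reaches 80% power with 10 patients in total. The stated sample size therefore belongs to a between-arm test, not to the test in 9.6.

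**2. False-positive rate of the paired test under a shared shift.** Assume no ginger effect and the same mean shift in both arms. With d = shift / SD of change, the chance of significance is P(|T| > t₀.₉₇₅,ₙ₋₁), where T is noncentral t with n − 1 degrees of freedom and noncentrality d√n. The between-arm test has an expected difference of zero, so it stays at 5%.

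| Test, one visit | d = 0.3 | d = 0.5 |
|---|---|---|
| Ginger arm, n = 16 (noncentrality 1.2, 2.0) | 0.203 | 0.465 |
| Both arms pooled, n = 32 (noncentrality 1.70, 2.83) | 0.376 | 0.782 |
| Between arms | 0.05 | 0.05 |

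**3. Either of two visits.** Section 9.6 tests Days 28 and 56 without choosing one. A simulation (200,000 runs, 16 per arm, assumed correlation 0.5 between the two changes) gives 0.320 and 0.639 for the ginger-arm paired test, against 0.092 between arms. The paired test with no shift also gives 0.092, so that part of the excess comes from two visits and the rest from the shift.

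**4. The same in ppb.** SD of change = SD × √(2(1 − ρ)), where ρ is the assumed test-retest correlation. Example: SD 37 and ρ = 0.5 give 37.0; a 10 ppb shift is d = 0.27, noncentrality 1.08, probability 0.173. SD 37 is the planning value in 9.2. The value 10 is the ± figure in 9.6, read here as an SD. Ginger arm, n = 16, one visit:

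| Shared shift | SD 37, ρ = 0.5 / 0.7 / 0.8 | SD 10, ρ = 0.5 / 0.7 / 0.8 |
|---|---|---|
| 4 ppb | 0.069 / 0.082 / 0.098 | 0.322 / 0.489 / 0.658 |
| 10 ppb | 0.173 / 0.257 / 0.360 | 0.962 / 0.998 / 1.000 |

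**5. Thresholds.** At a baseline of 40 ppb the two rules agree (10 ppb; 25% of 40 = 10). At 30 ppb they give 10 against 7.5. At 60 ppb they give 12 against 15.

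**The case against.** The best defence is that a between-arm comparison is plainly intended. The design is placebo-controlled, 9.3 defines the populations by arm and applies intention-to-treat to the primary analysis, and 9.2 sizes FeNO for two arms. On that view one sentence merely omits the name of a test. The intention is clear, and it makes the pooled reading the less likely one. But intention supplies no test, scale or visit, and the same section did write a two-sample test for PD20. The text and the sample size contradict each other.

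The size of the problem is also open to challenge. Section 9.6 describes FeNO in asthma as very stable over time, and a 14–21 day run-in on usual medication should reduce early drift. Enrolment spread over 12 months would dilute a seasonal shift. The ± 10 in 9.6 is not labelled as an SD, and a 10 ppb shared fall from 40 ppb would equal the plan's own 25% criterion. These points stand: the upper figures are extremes, and at SD 37 a 4 ppb shift gives only 7–10%. They do not make the paired test valid.

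Finally, the repaired test has little power for the effect named in the text of 9.2. A 20% fall from 74 ppb is 14.8 ppb. With 16 per arm and SD 37, a two-sample test has power of about 0.20; ANCOVA has about 0.24 at correlation 0.5 and 0.45 at 0.8. That is a sample-size limitation to acknowledge, not a reason to keep a test without a control group.

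**Conclusion.** The concern holds. Section 9.6 leaves a primary outcome without its randomised comparison, and the test it does name conflicts with the design, the populations and the sample size. This follows from the text alone.

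The size of the error depends on assumptions the documents do not settle: the shared shift, the SD of change and the correlation between visits. Across the values tried, a null treatment would give a significant ginger-arm result at one visit in anything from 7% of trials (4 ppb, SD 37, ρ = 0.5) to over 95% (10 ppb, SD 10). Shifts of 0.3 and 0.5 SD of change give 20% and 46%. The between-arm test stays at 5% throughout.

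The threshold mismatch is a separate, lesser point. It affects interpretation and changes no p-value.

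**What to change.** Replace the FeNO test in 9.6, before the analysis begins, with wording such as:

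> The primary FeNO analysis compares ginger with placebo at Visit 5 (Day 56) in all randomised subjects by ANCOVA, with treatment as factor and Visit 3 FeNO as covariate, reported as the adjusted mean difference in ppb with 95% CI. The Day 28 comparison is secondary. Paired within-arm changes are descriptive.

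The minimum repair is the two-sample t-test of change already planned for PD20, at one pre-named visit. ANCOVA is preferable because its variance is σ²(1 − ρ²) against 2σ²(1 − ρ) for change scores, a ratio of (1 + ρ)/2, or 0.75 to 0.90 for ρ from 0.5 to 0.8. A log scale is optional, but the 16 per arm was derived in ppb and would have to be re-derived.

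Add how randomised subjects without a Visit 5 value are handled, since Sections 8 and 10.3.4 provide for removal from the study. Separately, state one FeNO relevance threshold in 1.1, 3 and 9.6.

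The cost is wording. FeNO is already measured at Visits 3, 4 and 5, and no patients or procedures are added. The within-arm p-values lose confirmatory status.
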